The TC comparator arm options and doses are described in greater detail in Section 7.2 and treatment duration will be based on approved prescribing information and institutional standard practice. Guadecitabine will be given SC at a dose of 60 mg/m² in 28-day cycles. For the first cycle guadecitabine will be given for 10 days on Days 1-5 and Days 8-12 or on Days 1-10. The second cycle will be either the 5-day regimen (Days 1-5) or 10-day regimen (Days 1-5 and 8-12 or Days 1-10) based on assessment of disease response and hematological recovery at the end of Cycle 1. In subsequent cycles guadecitabine treatment will be for 5 days only (Days 1-5). Guadecitabine treatment should be given for at least 6 total cycles in the absence of unacceptable toxicity or disease progression requiring alternative therapy. Beyond 6 cycles, treatment should continue as long as the subject continues to benefit based on investigator judgment.

Treatment cycles are intended to be repeated every 28 days. However, treatment delays are permitted to allow normal count hematological recovery in the absence of PB blasts, particularly with more intensive treatment such as guadecitabine 10-day regimen, HiDAC, MEC, and FLAG/Ida. Visits will occur on treatment days, as necessary. In addition, during the first 3 cycles, visits will occur weekly on Days 8, 15, and 22, then on Day 15 in Cycles 4-6. In Cycles >6, visits will only occur on treatment days (if necessary), with study specified assessments on Day 1. Additional visits based on treatment effect and blood counts may be done at the investigator's discretion. Subjects will attend a safety follow-up visit after the last study treatment. For subjects who discontinue study treatment before Cycle 6, long term follow-up visits will occur monthly until 6 months after the start of study treatment and then every 3 months thereafter. For subjects who discontinue study treatment after Cycle 6, long-term follow-up will be every 3 months.

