7.3 Guidelines for Adjusting or Withholding Study Treatment

7.3.1 Guidelines for Guadecitabine

Guadecitabine study therapy is intended to be administered for a minimum of 6 total cycles.

Dosing for the first 2 cycles is described in Section 7.1.2. Timing of cycle initiation and dose level of guadecitabine starting at Cycle 3 will be guided by PB blast and neutrophil/platelet counts after the prior cycle, as indicated in Table 5, which describes dose modification based on Day 29 or later PB counts.

Table 5:Guadecitabine Dosing Adjustment Guideline Based on Peripheral
Blood Blasts and Counts (for Cycles ≥3)

Neutrophils	Peripheral	No Peripheral Blood Blasts								
Platelets	Blood Blasts Present	On Day 1 of Next Intended Cycle	Recovery After ≤1-Week Dose Delay	Recovery After >1-Week Dose Delay						
ANC ≥500/µL AND Platelets ≥50,000/µL	Full dose (5-day	Full dose (5-day regimen) on schedule	Full dose (5-day regimen) after recovery	Reduce 1 dose level after recovery (5-day regimen)						
ANC <500/µL OR Platelets <50,000/µL	regimen) on schedule	Consider dose delay or reduction								

For subjects with CRh, CRi or CRp for at least 2 cycles, guadecitabine treatment may be reduced 1 dose level at a time in each subsequent cycle to allow for normal counts recovery to levels of full CR (neutrophils $\geq 1000/\mu$ L and platelets $\geq 100,000/\mu$ L). The highest dose level that achieves normal counts recovery should be kept for subsequent cycles. Recommended reduced guadecitabine dose levels should be from 60 mg/m²/day to 45 mg/m²/day, then to 30 mg/m²/day, and then to 15 mg/m²/day with the Daily×5 regimen.

Subjects with highly proliferative disease between cycles could receive subsequent cycles earlier than the intended 28-day cycle interval (such subsequent cycles could begin any time after treatment is completed in the preceding cycle).

Beyond 6 cycles, treatment should continue at the dose level reached as long as the subject continues to benefit based on investigator judgment and subject response and tolerability.

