Laboratory Assessments	Screening ^f (D -14 to -1)					•	•	•						•		•	•		
Hematology ^m	X	X ^m				Х			Х	Х	X ^m						Х	X	Xc
Serum chemistry ⁿ	X	X ⁿ									X ⁿ							Х	
Urinalysis	X																		
Serum or urine pregnancy test ^o	X	Х									Х							Х	
Disease Assessments			1	-	1	1		1	1	1				-	1	1	1		
BM aspirate or biopsy ^r	X	Xr									Xr								Xc
Cytogenetics	X																		
Hospitalizations/Transfusions ^s	X	Х									Х							X	Xc
Subsequent anti-leukemic therapy																		х	Х
Disease progression status ^t																		X	Xc
Survival follow-up																		Х	Х

^a The Day 15 visit is not required after Cycle 6.

Safety follow-up visit: Must occur 30 (+7) calendar days after the last dose of study treatment or before the subject starts another anti-leukemia therapy for AML (except for hydroxyurea as specified in Section 7.4.1), whichever occurs first. If the subject cannot attend the clinic, the visit may be conducted by telephone to collect, at minimum, AE, hospitalizations/transfusions, subsequent anti-leukemic therapy, QOL responses and survival information. Safety follow-up visit may occur at the same time as treatment discontinuation only if decision to permanently discontinue treatment is made at least 30 days after last dose.

^c Long-term follow-up visits: Start after treatment discontinuation. Monthly (±7 days) visits are required for subjects who discontinue study treatment before Cycle 6, until 6 months after the start of study treatment. After monthly visits for at least 6 months, long-term follow-up visits will be every 3 months (±2 weeks) until death. The first long-term follow-up visit should occur 1 month or 3 months (whichever applies) after the safety follow-up visit or after the last dose of study treatment, whichever applies. Monthly and quarterly visits may be conducted by telephone if needed. Refer to Section 9.5.6 for the specific assessments to be performed at the long-term follow-up visits.

Astex Pharmaceuticals, Inc. Clinical Protocol SGI-110-06

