BM aspirate or biopsy: BM aspirate and/or biopsy differential count will be performed according to local standard practice. The screening aspirate must be collected within 28 days before starting study treatment. A biopsy should be done if no spicules are observed in the aspirate. Repeat the BM sample if not interpretable.

Perform BM aspirate/biopsy at screening and then at the end of Cycles 1, 3, and 6 (ie, on or at any time prior to Day 1 of Cycles 2, 4, and 7), unless PB shows persistence of \geq 5% leukemic blasts that excludes the possibility of a marrow response. Subjects who discontinue treatment before Cycle 6 Day 1 and before documented disease progression must undergo monthly response assessment until 6 months after the start of study treatment or until disease progression or relapse is confirmed, whichever is first. After Cycle 6, repeat BM aspirate/biopsy every 3 months for the first year on study; BM will be repeated every 6 months thereafter until PB or BM assessment shows disease progression or relapse.

- ^s Hospitalizations/Transfusions: Document all blood and platelet transfusions (blood product transfused and units) within 56 days before starting study treatment. Document all hospital admission and discharge dates and main reason for hospitalization, as well as all blood and platelet transfusions (blood product transfused and units), from Cycle 1 Day 1 and then monthly to 6 months after the first dose, then at every study visit until disease progression.
- ^t **Disease progression status:** For subjects who discontinue study treatment before disease progression is documented, PB and BM aspirate/biopsy assessments as described in footnote "r" should continue until disease progression or relapse is confirmed.

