9.5.6 Long-Term Follow-up

Long-term follow-up starts after subjects discontinue study treatment. Long-term follow-up visits will occur monthly (\pm 7 days) for subjects who discontinue study treatment before Cycle 6, until 6 months after the start of study treatment. After monthly visits for at least 6 months after the start of study treatment, long-term follow-up visits will be every 3 months (\pm 2 weeks) until death. The first long-term follow-up visit should occur 1 month or 3 months (whichever applies) after the safety follow-up visit or after the last dose of study treatment, whichever applies. Long-term follow-up visits may be conducted by telephone if needed.

At the **monthly** long-term follow-up visits, the following assessments are required unless they are refused by the subject. However, at a minimum, information on survival status must be collected.

- Health-related QOL (Appendix 2).
- Hematology and/or BM aspirate/biopsy: Subjects who discontinue study treatment before documented disease progression must undergo response assessments (PB or BM aspirate/biopsy) until disease progression or relapse is confirmed.
- Hospital admission and discharge dates (and the main reason for hospitalization), as well as all blood and platelet transfusions (blood product transfused and units) since the last visit.
- Subsequent anti-leukemic therapy (regimen and start date); for HCT, include time to stem cell engraftment.
- Survival follow-up (must be collected).

At the **quarterly** long-term follow-up visits, the following assessments are required unless they are refused by the subject. However, at a minimum, information on survival status must be collected.

- Health-related QOL (Appendix 2) until disease progression.
- Hematology and/or BM aspirate/biopsy: Subjects who discontinue study treatment before documented disease progression must undergo response assessments (PB or BM aspirate/biopsy) until disease progression or relapse is confirmed.
- Hospital admission and discharge dates (and the main reason for hospitalization), as well as all blood and platelet transfusions (blood product transfused and units) since the last visit until disease progression.
- Subsequent anti-leukemic therapy (regimen and start date); for HCT, include time to stem cell engraftment.
- Survival follow-up (must be collected).

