5.0 ANALYSIS SETS

5.1 Efficacy Analysis Set

Efficacy analyses will be based on intent-to-treat (ITT) principle. The Efficacy Analysis Set will include data from all subjects randomly assigned to study treatment. All data will be included and no subjects excluded because of protocol violations. For the analysis of efficacy data, subjects will be included in the treatment group according to their randomly assigned treatment.

For NDAOH, and health-related QOL by EQ-5D-5L, the primary analysis will include only the data collected during the first 6 months of the study because, during this study period, subjects are assessed monthly whether or not they are still on study treatment. Secondary analysis, if performed, may also include data beyond the first 6 months of the study (eg, over the entire study period until disease progression).

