7.3.2.3 Number of Days Alive and Out of the Hospital

The date of each hospital admission and discharge were collected for each subject for at least 6 months (and until disease progression for subjects who had not progressed during the first 6 months or until the subject died or withdrew consent prior).

The duration of each individual hospital stay in days (regardless of the reason for hospitalization) is calculated as:

Duration of individual hospital stay = date of discharge – date of admission

For a subject who was admitted and discharged on the same day, the duration of hospital stay will be 0. The total duration of all hospital stays in the first 6 months is the sum of the durations of all individual hospital stays occurring between date of randomization and Day 180. For ease of calculation, one month is defined as 30 days for analyses conducted in this study.

The NDAOH within the first 6-month period is calculated as:

NDAOH6M = 180 - total duration of all hospital stays - number of death days before Day 180

For subjects who died within the first 6-month period, the number of death days before Day 180 is calculated as:

Number of death days = (date of Day 180 - date of death)

For subjects who died on or after Day 180 the number of death days before Day 180 will be set to 0.

For subjects who were lost to follow-up within 6 months (expected to be a very small number), the NDAOH will be calculated conservatively assuming that the subject would have died the day after the last contact day.

The NDAOH6M will be summarized by treatment group and comparisons between the 2 treatment groups will be performed using an analysis of variance (ANOVA) model at an overall alpha level

of 0.05, as further described in Section 7.3.3. The variables used for stratification at randomization will be included in the analysis of variance model as fixed factors.

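### Monthly off-treatment visits depend on stopping before Cycle 6 rather than on Day 180, so the 6-month NDAOH and EQ-5D window is not fully covered and the passages on hospital data conflict

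*Protocol*

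**What the plan says.** SAP 5.1 limits NDAOH and EQ-5D to 6 months because "during this study period, subjects are assessed monthly whether or not they are still on study treatment". Protocol 11.2.2 gives the same reason.

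The visit schedule is narrower. Under Table 7 footnote c, monthly long-term "visits are required for subjects who discontinue study treatment before Cycle 6, until 6 months after the start of study treatment". Section 9.5.6 agrees, and footnote j applies the same condition to EQ-5D. Section 4.1 adds: "For subjects who discontinue study treatment after Cycle 6, long-term follow-up will be every 3 months". Neither rule names a subject who stops during Cycle 6. In 9.5.6 the monthly list asks for hospital dates with no progression limit. The quarterly list asks for hospital dates and "all blood and platelet transfusions (blood product transfused and units) since the last visit until disease progression", and it ends EQ-5D at the same point.

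Other passages point the other way. Footnote s asks for hospital dates "from Cycle 1 Day 1 and then monthly to 6 months after the first dose", with no Cycle 6 condition. SAP 7.3.2.3 states: "The date of each hospital admission and discharge were collected for each subject for at least 6 months". Protocol 9.1 asks for admissions every month in the first 6 months, but then repeats the before-Cycle-6 condition for hospitalizations after treatment stops.

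**The concern.** NDAOH is 180 minus recorded hospital days minus days dead. If a living subject's admissions are no longer collected, those hospital days silently become days alive and out of hospital. The only rule for incomplete NDAOH data (SAP 7.3.2.3) covers loss to follow-up, which does not describe a subject still in survival contact, and SAP 7.8 allows no other imputation.

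Similar subjects are also recorded differently. One who progresses and stops late in Cycle 5 is followed monthly for hospital dates to 6 months whatever the disease status. One who stops after starting Cycle 6 has no such visit. NDAOH is third among the secondary tests (SAP 7.3.3), so its data should be complete on the same terms for everyone.

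**Working it through.** The plan gives no figure for this point, so there is none to reproduce. The check is a day count, followed by a size under stated assumptions.

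**Inputs**
- Cycle length: "Treatment cycles are intended to be repeated every 28 days" (Protocol 4.1).
- Window: 6 × 30 = 180 days from randomization (SAP 7.3.2.3).
- Randomization to first dose: 0 to 7 days (Protocol 6.1).
- Safety follow-up visit: 30 to 37 days after the last dose, or sooner if new anti-leukemia therapy starts. It collects hospital stays since the last record, and EQ-5D, for every subject (Protocol 9.5.5).
- Last dosing day in Cycle 6: Day 5 (guadecitabine, decitabine), Day 7 (azacitidine), Day 10 (LDAC) (Protocol 7.1.2, 7.2).

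**Start of Cycle 6.** On schedule, with first dose on the day of randomization, 5 × 28 + 1 = Day 141, and 180 − 141 = 39 days remain.

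**Days left uncovered** = 180 − day of the last hospital collection, not below zero.

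| Course in Cycle 6 | Last dose | Safety visit on time | Uncovered | Uncovered if new therapy brings the visit to the day after the last dose |
|---|---|---|---|---|
| 5-day | Day 145 | Day 175–182 | 0–5 | 180 − 146 = 34 |
| 7-day | Day 147 | Day 177–184 | 0–3 | 180 − 148 = 32 |
| 10-day | Day 150 | Day 180–187 | 0 | 180 − 151 = 29 |
| Single dose only | Day 141 | Day 171–178 | 2–9 | 180 − 142 = 38 |

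A 7-day lag or delay brings the on-time figure to 0 for the three full courses. A cumulative delay of 39 days puts Cycle 6 at Day 180 and removes the gap.

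**Early cycles.** For guadecitabine subjects with highly proliferative disease, "such subsequent cycles could begin any time after treatment is completed in the preceding cycle" (Protocol 7.3.1). If each cycle began 7 days early (an assumption), Cycle 6 starts on Day 5 × 21 + 1 = 106. The last dose is Day 110, the safety visit Day 140–147, and 33 to 40 days stay uncovered even with that visit.

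These hospital days are lost only after progression. For a subject without progression, the next quarterly visit asks for stays since the previous one.

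**Shift in an arm's mean NDAOH** = p × u × h, where p is the share of the arm affected, u the uncovered days and h the fraction of those spent in hospital. The documents give none of these. Assumed: p = 2–15%, u = 5–38, h = 0.2–1.0.
- Low: 0.02 × 5 × 0.2 = 0.02 day.
- Middle: 0.10 × 25 × 0.5 = 1.25 days.
- High: 0.15 × 38 × 1.0 = 5.7 days.
- Over the grid p = 2, 5, 10, 15%; u = 5, 9, 25, 38; h = 0.2, 0.5, 1.0, the shift is 1 day or less in 36 of 48 combinations.

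Only the difference between the two arms' shifts enters the comparison. With about 150 subjects per arm (about 300 randomized 1:1) and an assumed SD of 60 days, its standard error is 60 × √(2/150) = 6.9 days. Half that SD (30) gives 3.5. The largest SD possible for a quantity between 0 and 180 (180/2 = 90) gives 10.4. A 1-day shift is therefore about 0.10 to 0.29 of a standard error.

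**EQ-5D.** The assessment near Day 6 × 28 + 1 = 169 is skipped. The safety visit supplies one on Day 175–187 for a full on-schedule course, or earlier if brought forward.

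**The case against.** The strongest reply is that the safety follow-up visit is mandatory, may be done by telephone, and carries no Cycle 6 or progression condition. That stands, and it closes most of the gap for an on-schedule subject. It does not close it when new therapy brings the visit forward or when cycles were started early.

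A second reply is that footnote s and the SAP already require hospital data to 6 months for everyone. This shows a conflict rather than a cure. Footnote c and 9.5.6 schedule no visit for those data, and the long-term hospitalization entry in Table 7 refers to footnote c. Equally, loss of data is not proven, because sites may have followed footnote s.

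Two stronger readings are tempting. One is that every Cycle 6 stopper loses up to 39 days, or that back-to-back early cycles leave about 140. The 39-day figure ignores the safety visit. So does the 140-day figure: with Cycle 6 on Day 36–40 that visit falls on Day 70–81, leaving 99 to 110 days, and five courses without a gap are a theoretical extreme.

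The other is that the error favours guadecitabine. This is plausible: guadecitabine is planned for at least 6 cycles, TC duration follows local practice, and early cycles are described for guadecitabine only. But the documents give no share reaching Cycle 6 by arm. Low-intensity TC and BSC subjects can reach it too, and recovery delays, expected particularly with intensive treatment such as the 10-day regimen, shrink the gap.

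Finally, NDAOH is tested only if OS, EFS and 1-year survival all succeed, in a trial whose enrollment was stopped for futility. EQ-5D is outside the hierarchy. Both facts limit the consequence.

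**Conclusion.** The point holds as a conflict between passages and a partly unsupported rationale. The schedule does not provide monthly assessment through 6 months for subjects who stop in or after Cycle 6 but before Day 180, and the NDAOH formula would score their unrecorded admissions as days out of hospital.

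The gap is 0 to 5 days for an on-schedule 5-day course. It becomes material, about 29 to 40 days, in progressed subjects whose safety visit came early or whose guadecitabine cycles were shortened as assumed. The effect on an arm mean is probably about 1 day or less under most of the assumed inputs, and reaches 5.7 days only when every input is at its highest. A tilt toward guadecitabine is possible but not established. About one EQ-5D assessment per affected subject is skipped.

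**What to change.** In the protocol, reconcile 9.1, Table 7 footnotes c, j and s, and 9.5.6 so that hospital dates and EQ-5D are collected to calendar Day 180 regardless of cycle number or progression. Correct the rationale in 11.2.2 to match.

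Enrollment closed in September 2018 and off-treatment survival follow-up ended at 20 January 2020, so the useful work is now mainly in the SAP:
- Correct the rationale in 5.1.
- Retrieve hospital dates to Day 180 from site records where possible.
- Derive for each subject the last date through which admissions were asked about, and list by arm the living subjects for whom it falls before Day 180.
- Add an NDAOH sensitivity analysis that does not score those days as out of hospital. One option is to count them all as not out of hospital in both arms, which gives the same arithmetic as the existing loss-to-follow-up rule.

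The cost is a few telephone contacts or record checks, one listing and one extra analysis. EQ-5D values not taken at the time cannot be recovered and should be reported as missing by arm.

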9.5.2 Screening and Baseline Procedures

After the investigator or sub-investigator confirms that a subject is eligible and willing to participate in the study, study center personnel will forward the appropriate documentation to the attention of the sponsor according to the Study Procedures Manual.

Bone marrow aspirate/biopsy samples may be collected within 28 days before Cycle 1 Day 1. Within 14 days before randomization, perform the following study procedures and tests:

- Written informed consent. The ICF must be signed and dated by the subjects before any study-specific samples are collected or study-specific procedures are initiated.
- Complete medical history, including demographics. Record disease history, including the date of initial diagnosis. Document concurrent medical signs and symptoms to establish baseline conditions.
- Record prior anti-leukemic therapies, including start and stop dates, best response and duration of response.
- Record all medications taken within 14 days before randomization.
- Complete physical exam including height and weight, and examination of body systems according to institutional standards.
- Vital signs include resting systolic/diastolic blood pressure, resting respiration rate, resting heart rate, and body temperature.
- Serum or urine pregnancy test: for women of child-bearing potential only. Results must be negative for the subject to be eligible for enrollment into the study.
- ECOG performance status (Appendix 1).
- Height measurement (for BSA calculation).
- All study-procedure-related AEs from the time of informed consent.
- Blood and urine sample collection for clinical laboratory tests (Table 8).
- •
- Adequate BM aspirate slide or biopsy to include touch prep slide, collected within 28 days before starting study treatment.
- Cytogenetic assessments performed at any time before randomization.
- Document all blood and platelet transfusions (blood product transfused and units) performed within 56 days before randomization.
- Investigator's confirmation of eligibility. Perform all necessary procedures and evaluations to document that the subject meets each eligibility criterion.

• Study treatment randomization, after eligibility is confirmed. Randomize as close as possible to the first dose of study treatment (on Cycle 1 Day 1). Treatment should start as soon as possible after randomization, and in all cases within 1 week.

Table 8:Clinical Laboratory Tests

